## **- Measurements**

### **A. Demography, physical examination and anthropometric data**

Demographic data collection (age), medication history taking, physical examination and measurement of weight and height with subsequent calculation of body mass index according the following formula:  $BMI = \frac{\text{Weight (kg)}}{\text{Height}^2 \text{ (m)}}$  will be done. Body surface area [Square root (weight "kg" X height "cm")/3600] and cumulative doses of chemotherapy will be also determined.

### **B. Blood sample collection and biochemical assessment**

Before starting the first chemotherapy cycle (baseline) and after the last chemotherapy cycle, 5 ml of venous blood will be withdrawn by antecubital venipuncture from each participant between 8:30 and 10:30 am into plain test tube and centrifuged at 3000 rpm for 10 min. The separated sera will be frozen at  $-80^{\circ}\text{C}$  until analysis of the biological parameters which include:

- Malondialdehyde (MDA) as oxidative stress marker (colorimetry).
- Tumor necrosis factor alfa (TNF- $\alpha$ ) as pro inflammatory marker (ELISA).
- Neurotensin (NT) as a potential marker for neuropathic pain (ELISA).
- Citrulline as a biomarker for mucositis (ELISA).

## **C. Assessment of Chemotherapy induced toxicities**

### **I. Clinical assessment of oxaliplatin induced peripheral neuropathy**

Clinical assessment of oxaliplatin induced neuropathy will be done through:

- The assessment of the severity of neuropathic pain through brief pain inventory short form "BPI-SF" worst item (16). Severity of neuropathic pain will be assessed at baseline and by the end of every two chemotherapy cycles.
- The implication of National Cancer Institute Common Terminology Criteria for Adverse Events (NCI-CTCAE, Version 5, 2017) for grading of neuropathy (17) at baseline and by the end of every two chemotherapy cycles.
- The use of Neurotoxicity- 12 item questionnaire score (Ntx-12) from the validated Functional Assessment of Cancer Therapy/Gynecologic Oncology Group "FACT/GOG-Ntx-12" (18) at baseline and by the end of every two chemotherapy cycles).

### **II. Clinical assessment of chemotherapy induced mucositis**

- Mucositis will be assessed at baseline and by the end of every two chemotherapy cycles through the use of common terminology criteria for adverse events "CTCAE, version 5.00, 2017" (17).

## **D. Assessment of participants' adherence, side effects and tolerability**

Pentoxifylline will be provided on biweekly basis and the participants' adherence will be assessed through counting the returned tablets. Participants will be followed-up by weekly telephone calls and direct meetings during chemotherapy cycles to assess their adherence and to report any drug related adverse effects. The adverse effects will be collected and graded according to the National Cancer Institute Common Terminology Criteria for Adverse events "NCI-CTCAE; version 5, 2017" (17). Participants will be considered non-adherent and excluded from the study if not consumed the provided tablets or lost the follow-up meeting at any time of intervention or changed regimen.

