## Patients and Methods

### **- Study design and treatment protocol:**

This study will be a randomized placebo controlled parallel study. Forty-eight eligible patients with stage II and stage III colorectal cancer will be scheduled to receive 12 cycles of folinic acid, fluorouracil and oxaliplatin (FOLFOX6 regimen). Patients will be recruited from the Oncology Department, Tanta University Hospital, Tanta, Egypt. Staging will be done according to the American Joint Committee on Cancer 7th edition staging. The patients will be randomized using according to the days of hospital admission into two groups:

**Group I (control group; n=24)** which will receive 12 cycles of FOLFOX-6 regimen plus placebo tablets twice daily.

The chemotherapy cycles will be received every 2 weeks and will be as follows:

**Day 1:** Oxaliplatin 85 mg/m^2 intravenous infusion in 250-500 mL 5% dextrose solution and leucovorin 400 mg/m^2 intravenous infusion in 5% dextrose solution both were given over 120 minutes at the same time in separate bags using a Y-line access, followed by 5-fluorouracil 400 mg/m^2 intravenous bolus given over 2-4 minutes, followed by 5-fluorouracil 2400 mg/m^2 intravenous infusion in 1000 mL 0.9% Sodium Chloride solution as a 46-hour infusion.

Additionally, Intravenous 5-HT3 antagonist plus pantoprazole will be administered to all participants before each cycle as prophylactic therapy against chemotherapy induced nausea, vomiting and mucositis. Furthermore, all participants will be submitted to complete blood count analysis before each chemotherapy cycle.

**Group II (Pentoxifylline group; n=24)** which will receive FOLFOX-6 regimen in addition to pentoxifylline 400 mg twice daily.

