**- Statistical analysis:**

- The collected data will be tabulated using Microsoft® Office Excel, 2019 (Microsoft Corporation).
- The statistical analysis will be carried out using SPSS statistical package version 26.0 (IBM corporation software group, USA).
- Data will be tested for normality using Shapiro-Wilk test or Kolmogorov–Smirnov test.
- Parametric data will be analyzed using Paired and un-Paired *t*-test to compare the means within the same group and to compare the means of the two groups respectively.
- Non- Parametric data will be analyzed using Mann Whitney U test to compare the means within the same group and to compare the means between groups.
- Categorical data will be analyzed using Chi-Square test.
- Fisher’s exact test will be used to analyses the reported adverse effects.
- Correlation between variables will be assessed using Pearson or Spearman correlation coefficient which appropriate.
- Data will be expressed as the mean  $\pm$  SD, medians, range, number and percent as appropriate.
- The significance level will be set at  $p \leq 0.05$ .

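### General adverse-event collection is worded as drug-related effects only, with no definition of drug or causality rule, so events put down to FOLFOX may go unrecorded before the arms are compared

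*Combined protocol and SAP*

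**What the plan says.** The general collection of adverse effects is described in section D (adherence, side effects and tolerability). The section opens with the study tablet: "Pentoxifylline will be provided on biweekly basis and the participants' adherence will be assessed through counting the returned tablets". It continues "Participants will be followed-up by weekly telephone calls and direct meetings during chemotherapy cycles", and states the purpose of these contacts as "to assess their adherence and to report any drug related adverse effects". The next sentence reads "The adverse effects will be collected and graded according to the National Cancer Institute Common Terminology Criteria for Adverse events". No causality scale, assessor or definition of drug is given.

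The Statistical analysis section says that Fisher's "exact test will be used to analyses the reported adverse effects".

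Three kinds of toxicity are measured separately, in both arms and with no attribution step:
- **Neuropathy** (section C.I): CTCAE is used "for grading of neuropathy (17) at baseline and by the end of every two chemotherapy cycles", with Ntx-12 and the BPI-SF worst-pain item on the same schedule.
- **Mucositis** (section C.II): "Mucositis will be assessed at baseline and by the end of every two chemotherapy cycles".
- **Blood counts** (Study design and treatment protocol): a complete blood count before every cycle for all participants.

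The design section also gives both arms FOLFOX-6, with placebo tablets in the control arm. All participants receive premedication "as prophylactic therapy against chemotherapy induced nausea, vomiting and mucositis".

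**The concern.** A concurrent placebo arm makes individual causality judgements unnecessary for the main safety question. If all events are counted in both arms, chemotherapy toxicity forms a shared background, and an excess in one arm points to the tablet or to its combination with FOLFOX. Asking for a causality judgement before an event is recorded gives up part of that advantage.

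The judgement is also a hard one here. The plan itself expects nausea and vomiting from chemotherapy in every participant, so a caller who hears of vomiting has a ready explanation other than the tablet. If the event is then not recorded, it cannot reliably be recovered later.

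The filter may also differ between arms. Allocation follows the day of hospital admission, so anyone who knows that day and the rule can infer the arm. The sections available describe placebo tablets but do not say that callers or assessors are blinded. What is at stake is the tolerability statement. Adverse effects are not among the listed endpoints, so the efficacy conclusions are not affected by this point.

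**Working it through.** The plan states no adverse-event figure, so there is none to reproduce. The check is of wording, followed by an illustration.

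**Step 1. Trace the chain.** Section D says what the contacts are to report (drug-related effects). Its next sentence collects and grades the adverse effects, which most naturally refers back to that set. The Statistical analysis section tests the reported effects. CTCAE, as used here, grades effects and does not assign cause. No section says that all events are recorded whatever their cause.

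**Step 2. What drug means.** Two readings are possible.
- *Study tablet.* Section D concerns tablets and adherence, and chemotherapy toxicity has its own section C. This is the more natural reading. Events put down to FOLFOX then fall outside what is to be reported.
- *Any drug, including FOLFOX.* The filter largely disappears, although relatedness to some drug must still be judged first. Two callers could read the sentence differently.

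**Step 3. What escapes the filter.** Neuropathy, mucositis and blood counts are measured in everyone. For blood counts the missing piece is a stated between-arm comparison, not the measurement. Events such as nausea and vomiting have no scheduled assessment that is independent of cause.

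**Step 4. Illustration.** The only inputs from the documents are 24 patients per arm and the 0.05 significance level. Event rates and recorded shares are assumed. If the same share *s* of episodes is recorded in both arms, whatever their true cause, then

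recorded rate = *s* × true rate; recorded excess = *s* × true excess.

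With assumed true rates of 50% (placebo) and 75% (pentoxifylline), the true excess is 25 points:
- *s* = 0.5: 25.0% and 37.5%, excess 12.5 points
- *s* = 0.2: 10% and 15%, excess 5 points
- *s* = 0.1: 5.0% and 7.5%, excess 2.5 points

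One patient in 24 is 1/24 = 4.2%, so 5 points is about one patient.

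Exact power of a two-sided Fisher test (24 per arm, p ≤ 0.05, all binomial outcomes enumerated):

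| Assumed true rates | Share recorded | Recorded rates | Power |
|---|---|---|---|
| 50% vs 75% | all | 50% vs 75% | 34% |
| | one-half | 25% vs 37.5% | 10% |
| | one-fifth | 10% vs 15% | 4% |
| 30% vs 70% | all | 30% vs 70% | 75% |
| | three-quarters | 22.5% vs 52.5% | 48% |
| | one-half | 15% vs 35% | 27% |
| | one-quarter | 7.5% vs 17.5% | 10% |

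**Step 5. Change the key assumption.** Step 4 treats attribution as wholly uninformative. Suppose instead that one-fifth of background episodes but all tablet-caused episodes are recorded. The rates become 0.2 × 50% = 10% and 10% + 25% = 35%. The 25-point excess is preserved and power is 46%, above the 34% with complete recording. The loss therefore depends on how poor attribution is.

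**The case against.** The strongest reply is that the wording does not exclude anything. Section D does not say *only*, does not define drug and contains no instruction to discard events, and its sentence on collection and grading carries no qualifier. Since oxaliplatin, fluorouracil and leucovorin are also drugs, a site could record chemotherapy effects and comply fully. This stands as a limit on the claim: events may be lost, but the plan does not require it. It does not remove the case for clear wording, because the narrower reading is the more natural one in its section.

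A reader might infer three stronger things, and the documents support none of them.
- *That harms resembling chemotherapy toxicity are lost as a class.* Neuropathy, mucositis and blood counts are measured without attribution. A low platelet count, for example, would be seen before the next cycle.
- *That sites would put most such events down to chemotherapy.* No section describes or predicts this. Nor do the documents say which harms pentoxifylline causes, so the overlap can be stated only as a possibility.
- *That the comparison is biased toward good tolerability.* Dilution is one possible outcome. A filter that differs by arm could create a difference as well as hide one, and informative attribution could preserve the excess (step 5).

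It is also fair to say that complete recording would not make the safety comparison strong. At 50% versus 75%, a trial of this size would miss the excess about two times in three even with every event recorded.

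**Conclusion.** The concern holds in a limited form. The plan's only general collection of adverse effects is framed by relatedness to an undefined drug, with no causality rule, and the between-arm test uses what was reported. Because both arms receive FOLFOX-6, individual attribution of events such as nausea and vomiting is unreliable. Some may go unrecorded, and the comparison may be diluted, or distorted if the arm can be inferred from the admission day. The gap is confined to events other than neuropathy, mucositis and blood-count abnormalities.

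The gap in the wording is clear from the text. Its consequence is plausible but not demonstrated. No size can be derived from the documents: the fall from 25 to 5 points, and from 34% to 4% power, rests on assumed rates, a recorded share of one-fifth, and attribution that carries no information. The change is worth making before recruitment because it is small and unrecorded events cannot reliably be recovered.

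**What to change.** In section D, replace the wording about drug-related effects with: *all adverse events, whatever the suspected cause, in both arms, from the first tablet to the last study assessment*. Keep CTCAE version 5 grading, and record suspected relationship (tablet, chemotherapy, other) as a separate field that does not decide whether an event is entered.

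In the Statistical analysis section, state that all-cause events are compared by arm with the Fisher's exact test already planned, including abnormalities in the blood counts already taken before each cycle. Present the subset judged related descriptively.

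The cost is one protocol sentence, one field on the form and a short addition to the analysis text. The contacts and visits are unchanged, as are treatment and clinical management. The downside is more events to record and higher reported rates in both arms, which the report should explain.

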**- The primary and secondary endpoints:**

The primary endpoint is the percentage of patients with peripheral sensory neuropathy grade  $\geq 2$ , the variation of 12-item neurotoxicity questionnaire (Ntx-12) total score and the variation in grades of mucositis. The secondary endpoint is the change in the serum concentrations of the measured biological markers.

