**- Sample size calculation:**

According to the results of previous studies, the total number of subjects required to detect the effect of neuro-protective drugs in patients received neuro-toxic chemotherapy was 41 patients with 5% significance, 80% statistical power and an attrition of 15 % (19, 20). In this context, during the current study, a total sample size of 41 patients in both arms will be sufficient to detect the effect. Assuming that the attrition rate will be 15 %, the initial sample size will be 48 patients in both arms with 24 patients in each arm.

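### Patients are excluded after allocation for non-adherence, a missed meeting or a regimen change, and no all-allocated analysis set or missing-outcome rule is defined; loss that differs by arm and outcome would bias the primary comparisons.

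*Combined protocol and SAP*

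**What the plan says.** Under adherence, side effects and tolerability (Measurements, section D), participants are "considered non-adherent and excluded from the study if not consumed the provided tablets or lost the follow-up meeting at any time". The sentence continues to its third trigger: "lost the follow-up meeting at any time of intervention or changed regimen". The only measurement behind the first trigger is that "adherence will be assessed through counting the returned tablets". No count or percentage marks the line between adherent and non-adherent, and a regimen change is not defined.

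The endpoint section has three primary measures. It opens with "The primary endpoint is the percentage of patients with peripheral sensory neuropathy grade" 2 or higher, then adds the change in the Ntx-12 "total score and the variation in grades of mucositis". No population or time point is attached to any of them. Sections C.I and C.II schedule the neuropathy, Ntx-12 and mucositis assessments "at baseline and by the end of every two chemotherapy cycles", so a patient who leaves early will usually have some data.

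The sample size section deals with loss only as a number to add: "Assuming that the attrition rate will be 15 %, the initial sample size will be 48 patients". The statistical analysis section lists tests, for example "Categorical data will be analyzed using Chi-Square test", together with software and a significance level. Nothing in the protocol names an intention-to-treat, all-allocated or per-protocol set, provides for follow-up after non-adherence, or says how a missing outcome is handled.

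**The concern.** Allocation supports a comparison only if the groups analysed are the groups allocated. Here a stated rule removes patients because of things that happen during treatment. It is plausible, though the protocol does not show it, that those things are tied to how well the tablets are tolerated or to the neuropathy and mucositis being measured. A regimen change is the clearest candidate.

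Exclusion could mean removal from the analysis, or an end to follow-up with earlier data kept. The protocol does not say which. Under either reading nothing keeps the patient in the comparison to the end. With no adherence threshold, the decision to exclude is also left to judgement while outcomes accumulate.

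Loss that is random or similar in both arms mainly costs power. Loss that differs by arm and by outcome biases the estimate, and the direction depends on who is lost. The mechanism applies to all three primary measures. Outcomes that were never collected cannot be recovered afterwards.

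**Working it through.** **The plan's own figure.** Inputs from the sample size section: 41 patients required, 15% attrition, 48 enrolled, 24 per arm. 41 / 0.85 = 48.2 and 41 × 1.15 = 47.15, so 48 is reproduced to within a patient. Conversely 48 × 0.85 = 40.8, so about 7 of 48 patients may be absent at the end. The 41 cannot be reproduced, because no event rate, SD or effect size is given.

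**Both directions are possible.** Suppose 12/24 events in each arm, so no true difference. If 7 event patients leave the pentoxifylline arm, the comparison becomes 12/24 (50%) v 5/17 (29%), a false 21-point benefit. If 7 event-free patients leave instead, it becomes 12/24 (50%) v 12/17 (71%), a false 21-point harm. Neither reaches significance (p = 0.19), but the estimate is wrong in both.

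**Grade ≥2 neuropathy, no true effect.** Assumptions: 50% true rate in both arms, 24 per arm, uncorrected chi-square, two-sided 5%, exact enumeration. If a share q of event patients is removed, the observed proportion is p(1−q) / [p(1−q) + (1−p)]. For p = 0.50, q = 0.3 gives 0.35/0.85 = 0.412 and q = 0.6 gives 0.20/0.70 = 0.286.

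| Exclusion pattern | Type I error |
|---|---|
| None | 6.0% |
| Random 15% in both arms | 5.3% |
| 30% of event patients, both arms | 5.2% |
| 20% of event patients in one arm, 10% in the other | 5.6% |
| 30% in one arm, 15% in the other | 6.3% |
| 30% in one arm only | 9.0% |
| 60% in one arm only (extreme) | 28% |

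The 30% one-arm case removes 0.5 × 0.3 / 2 = 7.5% of all patients. The 60% case removes 0.5 × 0.6 / 2 = 15%, so the whole attrition allowance would be event patients from one arm.

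**Grade ≥2 neuropathy, true effect.** Assumed 60% control v 25% pentoxifylline, same test. Removing 40% of event patients changes 0.60 to 0.36/0.76 = 0.474 and 0.25 to 0.15/0.90 = 0.167.

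| Exclusion pattern | Power |
|---|---|
| None | 73% |
| Random 15% in both arms | 64% |
| 40% of event patients, both arms | 57% |
| 40%, control only | 34% |
| 40%, pentoxifylline only | 88% |

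**Ntx-12, no true effect.** Assumptions: normal scores, unpaired t-test, 200,000 simulated trials per case, exclusions only among patients in the worse half. Type I error is 5.0% with nobody excluded and 5.0% with 30% of that half removed in both arms. It is 7.5% with 30% removed in one arm only (false difference 0.14 SD) and 19% with 60% removed in one arm only (0.34 SD, extreme). Mucositis grades were not calculated.

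**How far 7 absent patients can move one result.** Hypothetical 12/20 control v 5/21 pentoxifylline, with 4 control and 3 pentoxifylline patients lost:

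| The 7 counted as | Table | Chi-square p | Fisher p |
|---|---|---|---|
| Left out | 12/20 v 5/21 | 0.019 | 0.028 |
| All event-free | 12/24 v 5/24 | 0.035 | 0.069 |
| All events | 16/24 v 8/24 | 0.021 | 0.042 |
| Control events, pentoxifylline event-free | 16/24 v 5/24 | 0.001 | 0.003 |
| Control event-free, pentoxifylline events | 12/24 v 8/24 | 0.24 | 0.38 |

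There are 5 × 4 = 20 possible completed tables, not equally likely. Of these, 14 keep p ≤ 0.05 by uncorrected chi-square and 10 by Fisher's exact test.

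**The case against.** The strongest reply is that material inflation needs strong, nearly one-sided selection, which the protocol gives no reason to expect. The comparator is placebo, and at 30% v 15% or 20% v 10% of event patients removed, type I error stays at 6.3% or 5.6%. That is fair, and it limits what can be claimed about size. It does not clear the rule: at 30% v 15% the observed rates are 0.350/0.850 = 41.2% and 0.425/0.925 = 45.9%, a false difference of about 5 points that no analysis in the plan would detect or correct.

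Second, the error-rate and power figures delete the patient's outcome. If exclusion only ends follow-up, an event recorded earlier could still count and those figures would not apply. This stands as a limit on the figures. The defect remains, because later events in those patients go unobserved and the plan does not say which reading is meant.

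Third, the completed-table example would look fragile in any 48-patient trial with 15% missing data. That is also true. It shows how much rests on the missing-outcome rule, and it does not isolate harm from the exclusion sentence.

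Fourth, the 15% allowance might be thought to cover the loss. It replaces numbers and does not correct selection, and the sample size section does not tie it to this rule.

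Finally, keeping non-adherent patients dilutes the effect. If 15% of pentoxifylline patients reverted to the control risk, the assumed 25% would become 0.85 × 25% + 0.15 × 60% = 30.25%, and power with complete follow-up would be 58%, against 73% undiluted and 64% with random 15% loss. At 7.5% reverting it would be 66%. This is a real cost to state openly, but not a reason to exclude patients after allocation.

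**Conclusion.** The concern holds. The protocol contains an explicit exclusion rule that acts after allocation, and nothing elsewhere returns those patients to the analysis, so following the plan as written can bias the primary comparisons. This goes beyond missing detail and should be corrected before the data are analysed, ideally while excluded patients can still be assessed.

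The bias is conditional: it arises if exclusion differs by arm and relates to outcome. Its size and direction cannot be derived from the protocol. Under the assumed rates, effects run from negligible (similar or mildly different loss) to a type I error of 9.0% for neuropathy and 7.5% for Ntx-12 with 30% one-sided removal, and 28% and 19% at the extreme. These figures show what is possible and are not a forecast.

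**What to change.** Replace the exclusion sentence in section D with wording such as: *Participants who stop or miss study tablets, miss a visit or have their regimen changed remain in the study for outcome assessment where they can be reached, and are analysed in the arm to which they were allocated.* If the current sentence is also meant to govern the supply of study tablets, the sponsor should state that separately; this point concerns only assessment and analysis.

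In the statistical analysis section:

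- Make all allocated patients the primary analysis set.
- Assess at the planned visits, or at the matching calendar time once cycles no longer apply. Cycles are every 2 weeks, so every two cycles is about every 4 weeks.
- Keep all data recorded before discontinuation, and do not count missing later assessments as event-free.
- State a missing-outcome rule for each primary measure before the data are analysed. Add a sensitivity analysis covering all event-free, all events, and the opposite extremes by arm.
- Keep the adherent set as a secondary per-protocol analysis, with a defined tablet-count threshold and a definition of regimen change.
- Report discontinuations and reasons by arm.

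The cost is protocol and analysis wording plus a few calendar-time assessments. The change itself adds no patients, but dilution may lower power as shown above, and the sponsor should acknowledge that. Patients who cannot be reached stay missing and fall under the stated rule. The change does not repair allocation by day of admission, which is a separate weakness and limits what any all-allocated analysis can protect.
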